A more thorough appreciation of stroke and its etiologies is likely both to lead to better clinical care and to inform new directions for care at MNH. Participants will receive free head CT imaging to potentially identify unrecognized and untreated causes of stroke. This could lead to improved health knowledge and more selected treatment approaches and care.

At MNH, training and knowledge of stroke, clinical research, and neuroimaging will occur throughout this study. Neurological research and focused expert neurological care post-stroke are nearly non-existent in Tanzania. Therefore, initial care provisions for brain disorders will provide foundational knowledge of neurological care to health care workers. This is likely to lead to better medical care for future patients with stroke who are not involved in the study.

II. Specific Aims:

(1) To calculate the cognitive outcomes, as measured by the SIDSA and MoCA for 90 days post-stroke in 200 participants. (2) To collect medical history survey data from 200 participants. (3) To calculate other variables of interest to the study population, including motor recovery (Fugl Meyer, modified Rankin scale), depression (PHQ-9, Asberg Depression Scale), lab variables (serum sodium, ALT), and quality of life (Stroke Impact Scale).

III. **Subject selection:**

Both male and female subjects greater than 18 years old and subjects from any racial and ethnic group may be enrolled in the study. Tanzania is an ethnically homogenous country; nearly all residents are ethnically Tanzanian. Therefore, in practice we expect little to no enrollment of other ethnicities and races beyond Tanzanian Africans. Recruitment of an approximately 1:1 male to female ratio is expected. Total recruitment is aimed at 200 participants with new-onset acute ischemic or hemorrhagic stroke presenting at Muhimbili National Hospital (MNH) within 21 days of symptomatic onset.

No children will be enrolled in the study. The mechanisms of stroke in pediatric age groups are presumed to be very different (e.g. non- atherosclerotic) and are outside the scope of the study question.

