Participants will have initial cognitive capacity measured through the MoCA scale and IDEA scale, administered in English or Kiswahili per patient preference.

Study participants will be contacted within three days of the 30-, 60-, and 90-day time-points to schedule an in-person visit, either at the hospital or at the participant's home. At each study visit, participants will be evaluated for medication and evaluated for adverse side-effects through verbal inquiry on the part of the investigator; investigators will draw 10-15mL of blood, in order to perform sodium and hepatic enzyme labs; investigators will assess participant disability through the modified Rankin Scale (mRS).

Analysis of serum sodium and hepatic enzyme levels will be conducted at MNH. Blood samples will also be shipped to the US for analysis of biomarkers of post-stroke cognitive decline.

If participants are unable to be reached in person during the 30- and 60-day follow-up visits, they will be called by Tanzanian site investigators. During these calls, investigators will evaluate the mRS of the participant and will inquire about adverse side-effects. The 90-day follow-up will occur either at MNH or at participants' home, whichever location was indicated as preferable during the screening and consent process.

Study Design: This study will be an observational trial to determine cognitive outcomes for 90 days following acute ischemic/hemorrhagic stroke in Tanzania. 200 patients presenting to Muhimbili National Hospital (MNH) with acute stroke will be enrolled. Subjects will be followed at 30, 60, and 90 days. The study endpoint will be considered as completion of the 90-day follow-up. Subjects will be remunerated the Tanzanian Schilling equivalent of 50 USD.

Objectives: (1) To calculate the cognitive outcomes, as measured by the SIDSA and MoCA for 90 days post-stroke in 200 participants. (2) To collect medical history survey data from 200 participants. (3) To calculate other variables of interest to the study population, including motor recovery (Fugl Meyer, modified Rankin scale), depression (PHQ-9, Asberg Depression Scale), lab variables (serum sodium, ALT), and quality of life (Stroke Impact Scale).

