All 90-day assessments will be administered by senior site investigators, who will also take the final 10-15mL blood draw, evaluate participant mRS, and inquire about adverse events. Participants will receive a second MRI brain at 90-days and will be administered the MoCA and IDEA screens. As at baseline, the 90-day Fugl-Meyer assessment will be filmed and stored on an encrypted external hard drive. In the case of aberrant scores or difficulty scoring, the video will be shown to expert study staff for validation of the correct Fugl-Meyer score.

It is possible that during the 90-day raft of questionnaires, participants will endorse survey questions that indicate suicidality. In such cases, participants will be formally referred to the study-site neurologist for psychiatric care and thorough psychological evaluation. Participants

will be referred to the managing neurologist because the number of psychiatrists in Dar Es Salaam is very low.

It may be necessary to drop certain participants from the study. In such cases, Tanzanian site investigators will evaluate the participant's continued participation in the study according to the following drop criteria: (1) participants who develop a serious, non-stroke related disease, like cancer, that will alter their life or seriously affect their medicine regimen; (2) participants who die; (3) participants who are lost to follow-up, defined as not being available during three attempts at contact 3 days apart over the course of 9 days; (4) participants who are unconscious or bed-ridden, defined as having an mRS score of 5 or greater; and (5) participants who become pregnant.

If a participant meets any drop criteria, Tanzanian site investigators will send a proposal, in writing, to U.S. site investigators to withdraw the participant from the study. U.S. site investigators will respond within 24 hours. When approved by U.S. site investigators, the participant will be formally withdrawn from the study. In cases where a participant develops a serious non-stroke related disease, he or she will be referred to appropriate physicians at MNH. In cases of death, loss to follow-up, or unconsciousness, Tanzanian site investigators will make a reasonable attempt to discover the circumstances surrounding participant withdrawal. Participant withdrawal will be noted in a Withdrawal Log alongside a brief explanation.

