Payment will be provided to participants. Payment will be the equivalent of 50 USD, approximately 116,000 Tanzanian Shillings. We expect this amount to fully cover the costs of transportation to and from the MNH.

VI. Biostatistical Analysis:

Data will include stroke motor-function recovery, cognition, serum sodium and hepatic enzyme laboratories, and quality-of-life/depression data, which will be captured, respectively, through changes in the Fugl-Meyer motor assessment between study enrollment and completion, through the IDEA and MoCA assessments, and through both the Asberg Depressive Symptom and PHQ-9 questionnaires.

The number of participants has been chosen based on an estimated natural history from our pilot observation work. A post-stroke mortality of approximately 30% at 90 days is assumed. Of n=200 enrolled participants, 140 are assumed to be alive at 90 days.

VII. Risks and Discomforts:

Risks associated with blood draws: During venous blood draws the skin is pierced by a needle. Any insult to the skin can result in discomfort, pain, and bruising. There is a slight risk of infections associated with blood draws. Risks will be minimized through the use of established blood-draw safety protocols, including exclusive use of sterile needles and use of alcohol swabs to disinfect the skin area that the needle will pierce.

Risks associated with MRI: During MRI, patients can experience discomfort due to the loud noises and closely enclosed space of the machine. Risks will be minimized by explaining MRI procedures to patients. MRI is also known to be safe and used in routine stroke clinical care in the US.

Potential psychological stress/discomfort: There exists a risk of incurring psychological discomfort due to diagnostic questions about mood. Discomfort includes embarrassment, anxiety, panic, or depression. In the event of severe psychological distress, subjects will be promptly referred to appropriate mental health experts.

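### Drop criterion 4 can withdraw living participants on an mRS of 5 or more, an outcome of the study, and nothing requires their day-90 status, so day-90 results may describe milder survivors

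*Combined protocol and SAP*

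**What the plan says.** **Outcomes and endpoint.** Aim 1 in Section II, repeated as Objective 1 in Section V, reads: "To calculate the cognitive outcomes, as measured by the SIDSA and MoCA for 90 days post-stroke in 200 participants". Aim 3 includes the modified Rankin Scale (mRS). Under Study Design in Section V, "The study endpoint will be considered as completion of the 90-day follow-up".

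**Measurement.** Section V has the mRS assessed at the 30-, 60- and 90-day visits. At days 30 and 60 it may be obtained by telephone if the participant cannot be seen; no telephone option is given for day 90. Cognition is tested at baseline and again at day 90, when participants "will be administered the MoCA and IDEA screens".

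**Withdrawal.** Section V gives five drop criteria: serious non-stroke disease, death, loss to follow-up ("participants who are lost to follow-up, defined as not being available during three attempts at contact", with the spacing of attempts specified), criterion 4 ("participants who are unconscious or bed-ridden, defined as having an mRS score of 5 or greater"), and pregnancy. When a criterion is met, the Tanzanian site sends a written proposal to the U.S. site, and withdrawal is formal once approved. "Participant withdrawal will be noted in a Withdrawal Log alongside a brief explanation". Section IX adds administrative reasons such as withdrawn consent and nonadherence.

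**Numbers.** Section VI states: "A post-stroke mortality of approximately 30% at 90 days is assumed". It continues: "Of n=200 enrolled participants, 140 are assumed to be alive at 90 days". No other loss is mentioned.

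**The concern.** A participant can be removed because of the value of an outcome, before the time at which that outcome is to be reported. Criterion 4 selects on severity by definition, so those who leave are not a random part of the survivors. Someone withdrawn at day 30 or 60 contributes no day-90 mRS and no follow-up cognitive score, because cognition is not tested between baseline and day 90.

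This is a descriptive natural-history study, so the distribution of day-90 disability and cognition is the result itself. If the most disabled survivors are missing, recovery looks better than it was, and enrolling more participants under the same rule does not correct that.

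A smaller matter goes with it. Section VI gives a number alive, and a reader could take it for the number who will have a day-90 cognitive result.

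**Working it through.** **Inputs from the documents:** 200 enrolled; about 30% mortality at 90 days; 140 alive (Section VI). **Assumed for illustration:** the share *w* of survivors withdrawn under criterion 4 before day 90; a milder mRS group that truly holds half of survivors; and the share *L* of survivors without a day-90 result for any reason. The documents give none of these.

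**1. The plan's own figure.** 200 × (1 − 0.30) = 140. It reproduces exactly, with death as the only loss.

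**2. Which losses that figure covers.**

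| Source of loss | Where | Rate given |
|---|---|---|
| Death | Sections V, VI | about 30% |
| Serious non-stroke disease | Section V | none |
| Loss to follow-up | Section V | none |
| mRS 5 or greater | Section V | none |
| Pregnancy | Section V | none |
| Administrative withdrawal | Section IX | none |

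**3. Following one participant.** A survivor is found at mRS 5 at the day-30 visit. Criterion 4 is met, a proposal is sent and approved, and the log is completed. The day-30 mRS is known. No later step calls for vital status or mRS at day 90, and Section VI does not say whether or how the participant enters the results.

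**4. Effect on a reported mRS proportion.** Let the milder group hold 70 of 140 survivors (50%), and let none of those withdrawn belong to it. The reported proportion is 70 / [140 × (1 − *w*)], so the true value is multiplied by 1/(1 − *w*).

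| *w* (assumed) | Withdrawn | Reported | Factor |
|---|---|---|---|
| 5% | 7 | 70/133 = 52.6% | 1.05 |
| 10% | 14 | 70/126 = 55.6% | 1.11 |
| 15% | 21 | 70/119 = 58.8% | 1.18 |

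**5. Dependence on the zero-overlap assumption.** If *k* of 14 withdrawn would have recovered into the milder group by day 90, the report is (70 − *k*)/126. With *k* = 3 it is 67/126 = 53.2%. With *k* = 7 it is 63/126 = 50.0%, and the bias disappears. The overstatement therefore holds as long as those withdrawn recover into the milder group less often than survivors in general.

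**6. The number with a day-90 result.** The expected number is 140 × (1 − *L*): 133 at *L* = 5%, 126 at 10%, 112 at 20%. The 140 is itself an expectation. At exactly 30% mortality, chance alone gives about 127 to 152 survivors (95% binomial range), and an assumed mortality of 20% would give 200 × 0.80 = 160.

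**The case against.** **Withdrawal is discretionary and the safeguards are real.** Section V says only that dropping participants may be necessary, and each case needs approval. The mRS that triggers criterion 4 is known at that moment, and nothing says it is discarded. The Withdrawal Log keeps a reason. The site tries to learn the circumstances after death, loss or unconsciousness. Section IX has deaths reported as serious adverse events and a DSMB that looks at retention, completeness and premature withdrawals. All of this stands, and it makes the attrition visible. It does not supply the missing outcome: none of these steps requires a day-90 status after withdrawal or says how the participant is analysed, and the inquiry into circumstances does not name people who are conscious but bed-ridden.

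**The size is assumed.** This is correct. The rates in the working are illustrations. Also, mRS 5 may precede death, so these withdrawals need not all come on top of the 30%.

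**Stronger readings that the documents do not support.**
- *Aim 1 promises 200 day-90 results and contradicts Section VI.* The 200 can be read as the enrolled cohort: Section V says 200 are to be enrolled, cognition is also tested at baseline, and Section VI discloses the fall to 140. The denominator is unclear; it is not an arithmetic error.
- *The sample is too small.* No precision target or power is stated, so there is nothing for 200 or 140 to miss.
- *140 is a hard ceiling.* It is an expected count under an approximate mortality. Section III excludes the most severe presentations and allows entry up to 21 days after onset, and Section VI does not say whether the pilot group was similar.
- *Section IV implies that about half of survivors will be untestable.* That figure concerns independent consent at entry, partly because of hand weakness. It is not a rate for completing cognitive tests at day 90.
- *Criterion 4 conflicts with eligibility.* The entry criteria do not mention mRS, but entry and withdrawal rules may differ, and no contradiction is shown.

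**Conclusion.** The point holds as a matter of outcome-dependent withdrawal, and it should be addressed. Where criterion 4 withdrawals are approved before day 90, the reported day-90 mRS and cognition describe milder survivors. At an assumed 10% of 140 survivors, a true 50% is reported as 55.6%; over 5% to 15% the range is 52.6% to 58.8%. These figures assume that none of those withdrawn would have been in the milder group. For cognition no size can be given, and the direction rests on the assumption that severe disability goes with poorer scores.

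The secondary point is one of wording. The 140 is the expected number alive at about 30% mortality and leaves out every other route of loss. It should not be read as the expected number with a day-90 cognitive result. The documents do not show that N is inadequate.

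**What to change.** 1. For participants withdrawn under a drop criterion who still consent, record vital status and mRS at day 90 by telephone, extending the method already used at days 30 and 60. Include them in the day-90 mRS distribution. If the day-90 mRS is not obtained, use the mRS at withdrawal in a sensitivity analysis labelled as such.
2. Classify all 200 at day 90 as dead; alive and assessed; alive but not testable, with reason; withdrawn, by criterion; or lost. The Withdrawal Log supplies part of this. Report cognitive scores as applying to survivors assessed, beside this table and the baseline characteristics of assessed and unassessed survivors.
3. Word Aim 1 and Objective 1 as 200 enrolled, with day-90 cognition in those alive and assessed. In Section VI, give the expected number assessed as at most about 140 under the 30% assumption, and label any further loss rates as assumptions.

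No change to the drop criteria themselves is proposed. The cost is a few extra calls (14 in the 10% illustration), one table, one sensitivity analysis and protocol wording, with no extra participants. The stated expected number will look less favourable. The telephone check recovers mRS and vital status but not the missing cognitive scores, which is why item 2 limits what those scores are said to represent.

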All serious adverse events/experiences as defined will be reported to the project manager at MNH and then to MGH within 24 hours of the Tanzanian site's awareness, regardless of whether the Tanzanian investigator feels that the experience is related to the study or was expected. Within that 24-hour period, the site investigator in Tanzania will also complete a MedWatch FDA form 3500 (or modified version of this for the Tanzanian authorities) and email it to the MGH site. For AE or significant abnormal results that are identified during a visit, telephone call, or other study activity, the site staff will ensure that the information is available to the participant and his/her primary physician (should one exist). The number of patients with primary physicians in Tanzania is very low. As appropriate and permitted by the participant, the primary care physician will be notified by the research staff via written correspondence to ensure follow up. If the finding affects the participant's immediate safety (e.g. laboratory value far out of range), appropriate and immediate action will be taken by the site investigator to ensure the participant's wellbeing.

The site study staff will assess AEs at every point of contact with subjects by recording all voluntary complaints by the participant and by assessment of clinical features. All AEs will be recorded in a study Adverse Events log. The log will include the event term, onset date, resolution date, AE, and participation in the study. If a participant is withdrawn from the study, it will be recorded. Causality definitions will include the following: unrelated (no possible causation), unlikely (not reasonably related although a causal relationship cannot be ruled out), possibly (causal relationship uncertain), probably (high degree of certainty for a causal relationship), and definite (causal relationship certain).

Additionally, participants will be advised in the written consent form that they have the right to permanently discontinue the study medication and/or withdraw from the study at any time without prejudice and may be withdrawn from the study at the discretion of the Tanzanian site investigator or MGH principal investigator. Administrative reasons for participant withdrawal include: participant withdrawal of consent, request of investigator or PI, request of primary care physician, nonadherence to study procedures, protocol deviation, and premature termination of the study.

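### Withdrawal for nonadherence, protocol deviation or one failed contact window can end follow-up in an observational cohort, and the plan does not provide for collecting day-90 outcomes afterwards.

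*Combined protocol and SAP*

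**What the plan says.** Two parts of the protocol govern this kind of withdrawal.

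- **Section IX (Monitoring and quality assurance).** Participants "may be withdrawn from the study at the discretion of the Tanzanian site investigator or MGH principal investigator". The administrative reasons include a request by the investigator or PI and end with "nonadherence to study procedures, protocol deviation, and premature termination of the study".
- **Section V (Study Procedures).** Loss to follow-up is one of five drop criteria and is defined as "not being available during three attempts at contact 3 days apart over the course of 9 days". The definition does not say which visit it applies to. The site sends a written proposal, and then: "When approved by U.S. site investigators, the participant will be formally withdrawn from the study".

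For death, loss to follow-up or unconsciousness, the only later step is that "Tanzanian site investigators will make a reasonable attempt to discover the circumstances surrounding participant withdrawal". The protocol does not provide for outcome assessment after withdrawal and names no method for missing day-90 data.

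Several provisions limit loss to follow-up. Section IV collects an address and three further contact routes and requires participants to be geographically reachable. Section V allows the day-90 visit at the hospital or at home, and replaces a missed in-person visit at day 30 or 60 with a phone call that records the mRS and adverse effects.

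Section VI states: "Of n=200 enrolled participants, 140 are assumed to be alive at 90 days".

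**The concern.** Section V calls the study observational, and no intervention is described. Nonadherence to study procedures would then most naturally mean missed visits, refused blood draws or MRI, or incomplete testing. None of these is a reason to forgo a later outcome. A participant who refuses one procedure, or cannot be reached around day 30, may still be alive, willing and assessable at day 90.

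Once that participant is withdrawn, the plan has no route back to a day-90 assessment. Aim 1 concerns cognition over the 90 days after stroke. If people withdrawn on these grounds tend to be more disabled or more cognitively impaired, the retained group will look better than the cohort. The link is plausible: Section IV expects about half of eligible patients to be unable to consent independently because of language or motor deficits, and describes fluctuating lucidity in others.

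The two rules sit in different sections, so correcting one leaves the other in force.

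**Working it through.** **1. The plan's own figure.** Section VI gives 200 enrolled and about 30% mortality at 90 days. 200 × (1 − 0.30) = 140, which reproduces the stated number. Only death has been subtracted. The 140 counts survivors and makes no allowance for loss among them.

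**2. Can the contact rule operate before day 90?** The definition names no visit. Section V schedules contact at days 30, 60 and 90. The phone call at days 30 and 60 is itself a contact attempt, so it lowers the chance of three failures. It does not help someone already withdrawn. As written, a failed window at day 30 or 60 can lead to formal withdrawal.

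**3. Inputs that must be assumed.** The documents give none of the following:

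- w, the share of survivors withdrawn on these grounds whose day-90 outcome could otherwise have been obtained: 5%, 10%, 20%.
- d, how many MoCA points lower they would score than retained survivors: 2, 4, 6.
- SD of the MoCA: 5.

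**4. Formulas.** With retained mean R, the mean of all survivors is (1 − w)R + w(R − d) = R − wd. The retained mean is therefore too high by w × d. The number assessed is n = 140(1 − w), and SE = 5/√n. Bias equals the SE when d = SE/w.

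| w | n | SE | Bias, d = 2 | Bias, d = 4 | Bias, d = 6 | d at which bias = SE |
|---|---|---|---|---|---|---|
| 5% | 133 | 0.43 | 0.1 | 0.2 | 0.3 | 8.7 |
| 10% | 126 | 0.45 | 0.2 | 0.4 | 0.6 | 4.5 |
| 20% | 112 | 0.47 | 0.4 | 0.8 | 1.2 | 2.4 |

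Bias exceeds the SE in three of the nine cells: 10% with 6 points, and 20% with 4 or 6 points. In the middle case it is 0.4 against 0.45.

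**5. Precision.** For a proportion of 0.5, the 95% half-width is 1.96 × √(0.25/n). That is 8.3 percentage points at n = 140, 8.5 at 133, 8.7 at 126 and 9.3 at 112. The loss of precision is small; possible bias is the main issue.

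**The case against.** The strongest reply is that nothing here removes outcomes automatically. Section IX withdrawal is discretionary. Section V requires a site proposal and U.S. approval, and the DSMB described in Section IX reviews retention and data completeness and tracks premature withdrawals. Three attempts must fail, with extra contact routes available. This stands: a reader might infer that sicker participants lose their outcome by rule, and the text does not say so. The gap is permission to withdraw combined with silence about follow-up afterwards. These safeguards reduce how often that matters, but none of them provides for a day-90 assessment once withdrawal has been approved.

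A reader might also infer that these grounds select on severity. They do not do so by definition. The criteria that do are elsewhere in Section V: "participants who are unconscious or bed-ridden, defined as having an mRS score of 5 or greater" and "participants who develop a serious, non-stroke related disease, like cancer, that will alter their life or seriously affect their medicine regimen". Those are separate clinical criteria and are not addressed here. Because they may already remove the most disabled participants, a large MoCA gap in the remaining withdrawals is harder to support.

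A third tempting inference is that the study will miss a target of 140. Section VI counts people alive, and withdrawal does not change who is alive. Only the narrower point holds: no loss among survivors is allowed for.

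It can also be said that the absence of treatment is not certain, since Section IX mentions a study medication and Section V has participants evaluated for medication. The adherence wording may be left over from an interventional protocol. That is an internal inconsistency to be reconciled, and the documents describe no intervention that would give the wording a purpose.

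Finally, some of those withdrawn would have no day-90 data in any case, because they refuse or cannot be found. The share lost because of the wording is therefore smaller than the share withdrawn, and is unknown.

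**Conclusion.** The concern holds in a limited form. Two stated rules permit withdrawal on grounds that have no evident purpose in an observational study, and the plan does not provide for outcomes afterwards. Applying them can lose day-90 MoCA, IDEA, Fugl-Meyer and mRS values that were obtainable. That the loss would depend on disability or cognition is plausible but inferred.

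The size rests wholly on the assumed 5% to 20% withdrawn, a gap of 2 to 6 points and an SD of 5. On those, the retained MoCA mean is too high by 0.1 to 1.2 points, which is below the SE at the low and middle settings and above it only towards the upper end. The change is worth making because it is cheap and protects Aim 1; the figures do not show that the results would be seriously distorted.

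**What to change.** - **Section IX:** state that nonadherence to procedures and protocol deviations are logged and do not by themselves end outcome follow-up. Investigator discretion need not be removed; it is enough to separate stopping a procedure from stopping outcome collection.
- **Section V:** treat failed contact at day 30 or 60 as a missed visit. Still attempt the day-90 assessment unless consent has been withdrawn or one of the separate clinical drop criteria applies. Those criteria are left as they are.
- **Section VI:** report how many survivors lack each day-90 outcome, with reasons, and state that the 140 allows for death only.
- **Sections V and IX:** reconcile the medication wording with the observational design.

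The cost is protocol wording plus some further calls or home visits at day 90, for which Sections IV and V already provide the contact routes and the home-visit option.
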